10.5. Ethical Conduct of the Study

The study will be conducted in accordance with legal and regulatory requirements, as well as with scientific purpose, value and rigor and follow generally accepted research practices described in Guidelines for Good Pharmacoepidemiology Practices (GPP) issued by the International Society for Pharmacoepidemiology (ISPE¹³), European Medicines Agency (EMA), European Network of Centres for Pharmacoepidemiology and Pharmacovigilance (ENCePP¹³), and EU General Data Protection Regulation (GDPR¹⁴), as appropriate.

11. MANAGEMENT AND REPORTING OF ADVERSE EVENTS/ADVERSE REACTIONS

An adverse event (AE) is any untoward medical occurrence in a patient administered a pharmaceutical product and which does not necessarily have to have a causal relationship with this treatment. An AE can therefore be any unfavorable and unintended sign (including an abnormal laboratory finding, for example), symptom, or disease temporally associated with the use of a medicinal product, whether or not considered related to the medicinal product. The definition of an AE includes worsening of a pre-existing medical condition. A serious AE is any adverse drug reaction as defined above that:

- is fatal
- is life threatening (places the subject at immediate risk of death)
- requires in-patient hospitalisation or prolongation of existing hospitalisation
- results in persistent or significant disability/incapacity
- is a congenital anomaly/birth defect
- other significant medical hazard.

A serious adverse drug reaction is a serious adverse event that is considered related to the medicinal product.

A hospitalisation meeting the regulatory definition for “serious” is any inpatient hospital admission that includes a minimum of an overnight stay in a healthcare facility. “Other significant medical hazards” refer to important medical events that may not be immediately life-threatening or result in death or hospitalisation, but may jeopardise the patient or may require intervention to prevent one of the other outcomes listed in the definition above. Examples of such events could include allergic bronchospasm, convulsions, and blood dyscrasias, drug-induced liver injury, events that necessitate an emergency room visit, outpatient surgery, or other events that require other urgent intervention.

All AEs related to any *Pfizer product(s)* shall be reported to Pfizer Pharmacovigilance, Pfizer Limited, [name]. **Email Transmission:** [contact]; **Facsimile Transmission:** [name] (toll free); **Telephone Contact:** [name] (toll-free) or [name] (toll), by *the Principal Investigator at each centre or pH Associates* within 24 hours of discovery or notification. AE information must be recorded on the AE form emailed and/or faxed to **Email Transmission:** [contact] **Facsimile Transmission:** Pfizer Pharmacovigilance; [name] (toll free) or [name] (toll) **Telephone Contact:** 0845 300.

Adverse drug reactions for non-Pfizer products should be notified by the Principal Investigator at each centre to the appropriate Marketing Authorisation Holder and/or to the Medicines and Healthcare Regulatory Authority (MHRA).

All pregnancies occurring in female patients while taking Pfizer products, and all pregnancies occurring in female partners of male patients taking Pfizer products should be reported to **Email Transmission:** [contact]; **Facsimile Transmission:** [name] (toll free), [name] (toll) **Telephone Contact:** [name] (toll-free) or [name] (toll). Pfizer Pharmacovigilance, Pfizer Limited, [name] Email: [contact].

This study protocol requires human review of patient-level unstructured data; unstructured data refer to verbatim medical data, including text-based descriptions and visual depictions of medical information, such as medical records, images of physician notes, neurological scans, X-rays, or narrative fields in a database. The reviewer is obligated to report AEs with explicit attribution to any Pfizer drug that appear in the reviewed information (defined per the patient population and study period specified in the protocol). Explicit attribution is not inferred by a temporal relationship between drug administration and an AE, but must be

based on a definite statement of causality by a healthcare provider linking drug administration to the AE.

The requirements for reporting safety events on the non-interventional study (NIS) adverse event monitoring (AEM) Report Form to Pfizer Safety are as follows:

- All serious and non-serious AEs with explicit attribution to **any Pfizer drug** that appear in the reviewed information must be recorded on the eCRF and reported, within 24 hours of awareness, to Pfizer Safety using the NIS AEM Report Form.
- Scenarios involving drug exposure, including exposure during pregnancy, exposure during breast feeding, medication error, overdose, misuse, extravasation, lack of efficacy, and occupational exposure associated with the use of a Pfizer product must be reported, within 24 hours of awareness, to Pfizer Safety using the NIS AEM Report Form.

For these AEs with an explicit attribution or scenarios involving exposure to a Pfizer product, the safety information identified in the unstructured data reviewed is captured in the Event Narrative section of the report form, and constitutes all clinical information known regarding these AEs. No follow-up on related AEs will be conducted.

All the demographic fields on the NIS AEM Report Form may not necessarily be completed, as the form designates, since not all elements will be available due to privacy concerns with the use of secondary data sources. While not all demographic fields will be completed, at the very least, at least one patient identifier (e.g., gender, age as captured in the narrative field of the form) will be reported on the NIS AEM Report Form, thus allowing the report to be considered a valid one in accordance with pharmacovigilance legislation. All identifiers will be limited to generalities, such as the statement “A 35-year-old female...” or “An elderly male...” Other identifiers will have been removed.

Additionally, the onset/start dates and stop dates for “Illness”, “Study Drug”, and “Drug Name” may be documented in month/year (mmm/yyyy) format rather than identifying the actual date of occurrence within the month /year of occurrence in the day/month/year (DD/MMM/YYYY) format.”

All research staff members must complete the following Pfizer training requirements:

- “YRR Training for Vendors Working on Pfizer Studies (excluding interventional clinical studies and non-interventional primary data collection studies with sites/investigators)”.

These trainings must be completed by research staff members prior to the start of data collection. All trainings include a “Confirmation of Training Certificate” (for signature by the trainee) as a record of completion of the training, which must be kept in a retrievable format. Copies of all signed training certificates must be provided to Pfizer.

Re-training must be completed on an annual basis using the most current Your Reporting Responsibilities training materials.

11.1. Single Reference Safety Document

The InO Summary of Product Characteristics ¹⁵ will serve as the Single Reference Safety Document (SRSD) during the course of data collection part of the study, which will be used by Pfizer safety to assess any safety events reported to Pfizer Safety by the investigator during the course of this study.

The SRSD should be used by the investigator for prescribing purposes and guidance.

12. PLANS FOR DISSEMINATING AND COMMUNICATING STUDY RESULTS

The study will be reported according to the requirements of Strengthening the reporting of observational studies in epidemiology (STROBE)¹⁶.

Authorship of publications arising from the study will follow the 2015 guidelines proposed by the International Committee of Medical Journal Editors (ICMJE)¹⁷. All authors will meet the criteria for authorship, and all people who meet the criteria will be authors. Potential conflicts of interest will be disclosed. All authors will have:

- made substantial contributions to conception or design or acquisition of data, or analysis and interpretation of data; AND
- participated in drafting the article or revising it critically for important intellectual content; AND
- approved the final version to be published.

Each author will meet all of these conditions and all individuals meeting these criteria will be authors. Acquisition of funding, collection of data, or general supervision of the research group does not justify authorship. Each author will have participated sufficiently in the work to take public responsibility for appropriate portions of the content.

In the event of any prohibition or restriction imposed (e.g., clinical hold) by an applicable competent authority in any area of the world, or if the investigator is aware of any new

information which might influence the evaluation of the benefits and risks of a Pfizer product, Pfizer should be informed immediately.

In addition, the investigator will inform Pfizer immediately of any urgent safety measures taken by the investigator to protect the study patients against any immediate hazard, and of any serious breaches of this NI study protocol that the investigator becomes aware of.

14. LIST OF TABLES

Table 2: List of endpoints and variables required to address the objectives of the study

Table 3. Dataset to be collected according to study time points

15. LIST OF FIGURES

Figure 1. Schematic of study design

16. ANNEX 1. LIST OF STAND ALONE DOCUMENTS

Number	Document reference number	Date	Title
1	 B193 InO_Incl_Excl_criteria	15 08 2018	Inclusion and exclusion criteria for InO CUP
2	 INO1_Inotuzumab_rr_Phpos and neg_Bcell_I	06 09 2018	Inclusion and exclusion criteria for InO NHS Commissioning for adults

17. ANNEX 2. ADDITIONAL INFORMATION

Table 4. Dataset to be collected according to study time points

Variables	Study time points				
	Pre-index observation period	Baseline	Index date	Post-initiation observation period	Other
Date of birth (MM/YY)					✓
M/F					✓
ECOG performance status		✓			
InO first cycle: • dates of infusion • doses administered at each date, if dose is modified add reason for modification • date of end of cycle number • if decision taken to discontinue treatment: date discontinuation, reasons			✓	✓	
InO second cycle: • dates of infusion • doses administered at each date, if dose is modified add reason for modification • date of end of cycle number • if decision taken to discontinue treatment: date discontinuation, reasons					
InO additional cycles: • cycle number • dates of infusion • doses administered at each date, if dose is modified add reason for modification • date of end of cycle number • if decision taken to discontinue treatment: date discontinuation, reasons					
Response to InO treatment: • Treatment cycle number • Date response recorded • number of days into cycle response recorded					

PFIZER CONFIDENTIAL

Variables	Study time points				
	Pre-index observation period	Baseline	Index date	Post-initiation observation period	Other

 • CR, CRi, no response, progression • MRD negative, MRD positive 					
If CR/CRi response to InO treatment is not recorded in patient's medical notes for a specific cycle , then collect the following at time closest to the end of cycle to be able to infer CR/CRi and MRD negativity (see Annex 2 for operational definition):					

 • Cycle number • platelets levels • ANC levels • peripheral leukaemic blasts • bone marrow blasts • Ongoing extramedullary disease in the visceral organs, lymph nodes, and the central nervous system: Yes/No (interval from date started to date resolved needs to include date of end of cycle) 					
If MRD negativity response to InO treatment is not recorded in patient's medical notes for a specific cycle , then collect the following at time closest to the end of cycle to be able to infer CR/CRi and MRD negativity (see Annex 2 for operational definition):					

 • Cycle number • PCR results providing percentage of leukaemic cells in bone marrow nucleated cells • Or alternatively, immunophenotyping by flow-cytometry results providing percentage of leukaemic cells in bone marrow nucleated cells 					
ALL diagnosis: • Date of first diagnosis.	✓	✓			

INOTUZUMAB
X9001222 NON-INTERVENTIONAL STUDY PROTOCOL
V1.0, 18 July 2019

Variables	Study time points				
	Pre-index observation period	Baseline	Index date	Post-initiation observation period	Other

 Phase of disease at receipt of Inotuzumab CR, 1st relapse, 2nd relapse, 3rd relapse, 4th or greater relapse CD22-expression test results: positive/negative Cytogenetic test result: MLL- AF4; BCR-ABL; low hypodiploid/near triploidy; complex karyotype e Relapsed at index date: Yes/No Refractory at index date: Yes/No 					
Liver diseases diagnosed prior to index date: 
 Name date diagnosis Diagnosed before/after ALL diagnosis at index date, ongoing / resolved 	✓	✓			
Full blood counts, date, result (including unit) for: 
 platelets ANC 		✓	✓		
Liver function tests: date, result and ULN for: 
 ALT AST ALP Bilirubin Albumin gamma glutamyl transferase. 		✓	✓	✓ for ALT, AST and bilirubin in patients with follow-up HSCT, at time of follow-up HSCT (up to 3 months before)	
Peripheral blood blast counts of patients				✓ in patients with	

PFIZER CONFIDENTIAL

INOTUZUMAB
X9001222 NON-INTERVENTIONAL STUDY PROTOCOL
V1.0, 18 July 2019

Variables	Study time points				
	Pre-index observation period	Baseline	Index date	Post-initiation observation period	Other
				follow-up HSCT, at time of follow-up HSCT (up to 3 months before)	
ALL relapses prior to InO: 
 • date of relapses • Name, start and stop dates, and best response to treatment for relapses prior to InO (list to be determined and may include: fludarabine- and anthracycline-containing regimens, blinatumomab) 					
Treatment history for ALL (all since diagnosis) prior to InO: 
 • 1st line chemotherapy according to national trial or treatment guideline • Blinatumomab treatment • Number of lines of salvage therapy • Prior HSCTs: number (0, 1, 2, ≥ 3) and type of conditioning regimen for each HSCT: high-dose myeloablative, reduced-intensity, nonmyeloablative • CAR T-cell therapies: number (0, 1, ≥ 2) 	✓	✓			
ALL refractory prior to InO: 
 • Name, start and stop dates, and best response to treatment prior to InO 	✓	✓			
Concomitant medication to InO		✓ (if	✓	✓	

PFIZER CONFIDENTIAL

Variables	Study time points				
	Pre-index observation period	Baseline	Index date	Post-initiation observation period	Other
treatment: • Azole antifungal therapy including fluconazole, voriconazole, itraconazole and posaconazole: date started, date end		medication during InO treatment)			
AEs: name, date start, date end, grade, treatment given and response to treatment: • Documented diagnoses of VOD/SOS • grade 3/4 TRAEs affecting the lung, cardiac system, or kidney		✓		✓	
For each HSCT after initiation of InO: • date • InO treatment completed at HSCT: Yes / No • Conditioning regimens prior to HSCT including Busulfan other alkylating agents (names and date start, date end); full intensity / reduced intensity conditioning • Response to HSCT: CR, CRI, progressive disease, stable disease, alive/dead after HSCT				✓	
Chemotherapy treatment after initiation of InO: • name, regimen, start date • Response to chemotherapy treatment: CR, CRI, progressive disease, stable disease, alive/dead at end of treatment				✓	
CAR-T cell therapy after InO: • start date • response to CAR-T cell therapy: CR, CRI, progressive disease, stable disease, alive/dead at end of treatment				✓	
Patient status at the end of data collection period (alive/dead) • date of death / last clinic visit • Cause of death • If not known (i.e. lost to follow-up),				✓	

Variables	Study time points				
	Pre-index observation period	Baseline	Index date	Post-initiation observation period	Other
date of last recorded hospital visit.					

Note: All dates are DD/MM/YYYY for all patients, except for date of birth (MM/YY). If dates are not available as DD/MM/YYYY, dates will be recorded as MM/YYYY instead.

List 1. Operational definitions for clinical endpoints

Salvage therapy: therapy initiated in patients in whom initial induction therapy does not achieve remission (refractory ALL) or patients who entered remission and then subsequently relapsed (relapsed ALL), with the aim to induce remission of ALL.

Complete Remission (CR): defined as documented in medical records or (if unavailable in the records) as < 5% blasts in the bone marrow and the absence of peripheral blood leukaemic blasts, full recovery of peripheral blood counts (platelets $\geq 100 \times 10^9/L$ and absolute neutrophil counts (ANC) $\geq 1 \times 10^9/L$) and resolution of any extramedullary disease.

Complete Remission with incomplete haematological recovery (CRi): defined as documented in medical records or (if unavailable in the records) as < 5% blasts in the bone marrow and the absence of peripheral blood leukaemic blasts, incomplete recovery of peripheral blood counts (platelets $< 100 \times 10^9/L$ and ANC $< 1 \times 10^9/L$) and resolution of any extramedullary disease.

Minimal Residual Disease (MRD) negativity: patients with ALL may be in remission (CR/CRi) although they may still harbour a large number of undetected malignant cells (MRD), and as such may be more susceptible to relapse. MRD describes diseases that can be diagnosed by methodology other than conventional morphology, and includes molecular methods like PCR, or immunophenotyping by flow-cytometry¹⁸. MRD negativity will be defined as documented in medical records or (if unavailable in the records) as leukaemic cells comprising $< 1 \times 10^{-4}$ ($< 0.01\%$) of bone marrow nucleated cells.

CR/CRi Rate: proportion of patients who achieve CR/CRi at the end of treatment with InO.

MRD negativity Rate: the proportion of patients in whom MRD-negative status is observed at the end of treatment with InO (2-3 cycles of 3-4 weeks each in patients proceeding to follow-up HSCT, and up to 6 cycles of 3-4 weeks each otherwise).

Overall Survival (OS): time from index date to death. Patients will be censored at the end of the post-index observation period.

Relapse Free survival (RFS): time from index date to earliest date of the following events: death, progressive disease (including objective progression, relapse from CR/CRi, treatment discontinuation due to global deterioration of health status), and start of new induction therapy or post-therapy HSCT without achieving CR/CRi; as documented in medical records (if unavailable, infer using definitions above). Patients will be censored at the end of the post-index observation period.

Salvage therapy: Therapy initiated in patients in whom initial induction therapy does not achieve remission (refractory ALL) or patients who entered remission and then subsequently relapsed (relapsed ALL), with the aim to induce remission of ALL.

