Analyses will be performed by pH Associates using Stata (StataCorp LLC) and R statistical software. Data from the selected sites will be pooled for analysis. Data will be analysed according to a pre-defined statistical analysis plan that will be finalised before data collection is completed.

Descriptive statistics (numbers, percentages, means, standard deviations, medians, quartiles, minimum, maximum, number of missing and non-missing values), as appropriate to the data collected, will be used to describe baseline demographic and clinical characteristics, treatment pathway, outcomes and TRAEs for the overall study population. Ninety-five percent confidence intervals (95% CI) for CR/CRI rates and MRD negativity rates will be estimated using an exact Poisson regression. Patients who are still alive and have not progressed at the last visit date without clinical evidence of progression will be censored. Median time to CR/CRI, and median OS and RFS, and corresponding 95% CI, will be estimated using the Kaplan-Meier method.

CCI

A data analysis plan that further details the output, including table shell, to be included in the study report will be provided in a separate document, prior to data analysis.

Data collection will commence from the date relevant approvals from each of the participating centres are in place to conduct the study, and is anticipated to last for approximately four months

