The CR/CRI rate will be estimated as the proportion of patients who achieve CR/CRI divided by the total number of patients completing treatment with InO (defined as patients with a recorded date of discontinuation of InO). The MRD negativity rate will be defined as the proportion of patients in whom MRD-negative status is observed, among patients in whom MRD negativity status has been assessed, at any time until the end of treatment with InO (defined as the date of recorded discontinuation of InO). Patients who have not completed treatment with InO will not be included in CR/CRI rate and MRD negativity rate estimations. Date of 95% confidence intervals (CI) for CR/CRI rates and MRD negativity rates will be estimated using the Clopper-Pearson method. OR, RFS and NRM will be implemented according to their definition.

CCI

Where dates are ambiguous because of missing day and/or months, standard imputation will be applied: where day is missing the 15th of the month will be assumed; where both day and month are missing the 1st July will be assumed. Where data other than dates are missing from the original medical record, the affected analyses will be conducted using only the results of those patients with data available and the number included in each analysis will be stated. The percentage of data missing will be reported for each study variable. Note that the multivariate model will only include those patients with non-missing values for all covariates.

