10.1.4. Analysis for Binary Endpoints

Most binary endpoints will be summarized using frequency tables with numbers, percentages and the number of missing and non-missing values.

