Total duration of treatment with InO will be summarised as a quantitative variable (see [Section 10.1.1](#)); measures of central tendency (mean and median) and dispersion (standard deviation, interquartile range [IQR] and range) and the number of non-missing and missing values will be calculated. The number of cycles of InO per patient, the number of interrupted cycles of InO, doses of InO prescribed and the modification of doses of InO will be summarised as ordinal variables (see [Section 10.1.3](#)). Reasons for interruption and modification of InO cycles andazole antifungal therapies concomitant to InO treatment will be summarised as categorical variables (see [Section 10.1.2](#)). The proportion of patients who temporarily or permanently stopped InO treatment due to an AE will be presented as proportions and percentages.

10.2.3. Secondary Objective 2

To summarise CR/CRi rates following initiation of InO, overall and according to the number of salvage therapies received prior to InO initiation.

The CR/CRi rate will be estimated as the proportion of patients who achieve CR/CRi divided by the total number of patients completing treatment with InO (defined as patients with a recorded date of discontinuation of InO). Patients who have not completed treatment with InO or do not have a recorded discontinuation date will not be included. Patient response to treatment will be presented as a binary variable (see [Section 10.1.4](#)). Response rates will be presented overall and by number of salvage therapies in the pre-index observation period (0,1, ≥ 2). Kaplan-Meier analysis will be utilised to analyse time to CR/CRi and the median time to CR/CRi, as well as 95% CI, will be calculated using the Kaplan-Meier method and presented as per [Section 10.1.5](#).

10.2.4. Secondary Objective 3

To summarise MRD negativity rates following initiation of InO and describe the number of cycles of InO needed to attain MRD negativity.

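### The CRi count rule leaves one-lineage recovery unclassified, and the 95% CI for the CR/CRi rate has two conflicting methods, one with limits above 100%

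*Protocol*

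**What the plan says.** **Response definition.** In the protocol, Annex 2, List 1, CR is "defined as documented in medical records or (if unavailable in the records) as < 5% blasts in the bone marrow" together with no peripheral blasts, resolved extramedullary disease and "full recovery of peripheral blood counts (platelets $\geq 100 \times 10^9/L$ and absolute neutrophil counts (ANC) $\geq 1 \times 10^9/L"). CRi has the same marrow, blood and extramedullary conditions, but with "incomplete recovery of peripheral blood counts (platelets $< 100 \times 10^9/L$ and ANC $< 1 \times 10^9/L"). The counts are a fallback for responses missing from the notes. The Annex 2 data table provides for that: if CR/CRi is not recorded for a cycle, sites must "then collect the following at time closest to the end of cycle to be able to infer CR/CRi and MRD negativity". The SAP does not restate the count criteria.

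**Confidence interval.** The protocol abstract says that 95% intervals "for CR/CRI rates and MRD negativity rates will be estimated using an exact Poisson regression". Protocol section 9.7 says that intervals "for CR/CRI rates and MRD negativity rates will be estimated using the Clopper-Pearson method". SAP 10.1.4 says only: "Most binary endpoints will be summarized using frequency tables with numbers, percentages and the number of missing and non-missing values". SAP 10.2.3 adds: "Patient response to treatment will be presented as a binary variable". It gives a 95% CI for the median time to CR/CRi but not for the rate. SAP 10.2.4 gives no interval for MRD negativity, and the summary table in SAP 10.2.11 gives none for either rate.

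**The concern.** The two count rules are not complements. The opposite of both counts being recovered is that at least one is not, but the CRi rule requires that neither is. The name of the category and its wording (incomplete recovery) cover a patient with one count still low; the bracketed thresholds exclude that patient.

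The classification is used in four places:

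- the CR/CRi rate, overall and by number of prior salvage therapies;
- time to CR/CRi;
- MRD negativity, because SAP 10.2.4 now limits its denominator to patients who achieved CR/CRi;
- RFS, where new induction therapy or a transplant without CR/CRi counts as an event. Annex 2 says this may be inferred from the definitions above it. A one-lineage responder who goes to transplant could therefore be scored as an RFS event on the transplant date.

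On the interval, two sections of the same protocol version disagree, and the SAP, to which section 9.7 defers for detailed methods, does not settle it. A response rate is a binomial proportion. A Poisson interval treats the count as unbounded, so it is too wide when the rate is high and can pass 100%. With about 25 patients and no hypothesis test, the interval is what tells a reader how much the rate can support.

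**Working it through.** The documents state no expected count or interval for this study's CR/CRi rate, so there is no planned figure to reproduce.

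**Inputs**
- Sample size: about 25 (protocol 9.5). The denominator is patients with a recorded discontinuation date (protocol 9.7), so it may be smaller.
- Illustrative rate: 20/25 = 80%. This is an assumption, chosen to be close to the 80.7% CR rate that protocol section 7 quotes from the phase III trial.
- Smallest subgroup analysed: n > 5 (SAP 7.3), so 6 patients.

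**Step 1: count rules.** The four combinations below are for a patient who already meets the blast and extramedullary criteria (counts ×10⁹/L).

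| Platelets | ANC | CR rule | CRi rule as written | CRi rule with *or* |
|---|---|---|---|---|
| ≥100 | ≥1 | yes | no | no |
| ≥100 | <1 | no | no | yes |
| <100 | ≥1 | no | no | yes |
| <100 | <1 | no | yes | yes |

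Two of the four combinations have no category. For example, platelets 150 with ANC 0.6 is neither CR nor CRi.

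**Step 2: effect on the rate.** With 25 patients, each one lost costs 1/25 = 4 points. Starting from 20/25, with Clopper-Pearson limits:

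| Responders lost | Rate | 95% CI |
|---|---|---|
| 0 | 20/25 = 80% | 59.3% to 93.2% |
| 1 | 19/25 = 76% | 54.9% to 90.6% |
| 2 | 18/25 = 72% | 50.6% to 87.9% |
| 3 | 17/25 = 68% | 46.5% to 85.1% |

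**Step 3: the two intervals, for x responders out of n.**
- Exact Poisson, taken as an intercept-only model with n as exposure: lower = χ²(0.025; 2x)/(2n), upper = χ²(0.975; 2x+2)/(2n).
- Clopper-Pearson: lower = Beta(0.025; x, n−x+1), upper = Beta(0.975; x+1, n−x).

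At x = 20, n = 25:
- Poisson: 24.43/50 = 48.9% and 61.78/50 = 123.6%; width 74.7 points.
- Clopper-Pearson: Beta(0.025; 20, 6) = 59.3% and Beta(0.975; 21, 5) = 93.2%; width 33.9 points.
- Ratio of widths: 74.7/33.9 = 2.2.

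| x/n | Exact Poisson | Clopper-Pearson |
|---|---|---|
| 10/25 (40%) | 19.2% to 73.6% | 21.1% to 61.3% |
| 15/25 (60%) | 33.6% to 99.0% | 38.7% to 78.9% |
| 16/25 (64%) | 36.6% to 103.9% | 42.5% to 82.0% |
| 20/25 (80%) | 48.9% to 123.6% | 59.3% to 93.2% |
| 5/6 (83%) | 27.1% to 194.5% | 35.9% to 99.6% |

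At n = 25 the Poisson upper limit first passes 100% at 16 responders. At 10/25 it stays below 100%, but the interval is still (73.6 − 19.2)/(61.3 − 21.1) = 54.4/40.2 = 1.35 times as wide. In smaller groups the limit passes 100% sooner: from 4/10 and from 2/6.

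**The case against.** The strongest reply concerns weight, not text.

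- **The count rule is only a fallback.** It applies when the notes do not state the response. Inference is per cycle, and Table 1 and the SAP ask for response by the end of InO treatment. On that reading a patient is lost only if no cycle has a documented CR/CRi and no cycle meets either count rule. This stands: 4 points per patient is the effect of each patient actually lost, and the number lost cannot be estimated from the documents.
- **Coding is not specified.** No section says that a patient meeting neither rule is a non-responder, and an abstractor guided by the words rather than the thresholds could record CRi. This also stands, but it means that two abstractors could classify the same patient differently. The eCRF options and collection guidelines might resolve it, but they are not part of these documents.
- **Poisson appears only in the abstract.** Section 9.7 already has the right method, and the SAP neither adopts Poisson nor withdraws Clopper-Pearson. That makes the correction easy, but the contradiction remains, and the document meant to govern the analysis is silent.
- **Response is a secondary objective** in a descriptive study, and protocol 9.9 already warns of wide intervals. That is fair on priority. The warning also shows that the protocol expects these intervals to be reported.
- **The effect on MRD negativity has no fixed direction.** An excluded patient leaves both the CR/CRi numerator and the MRD denominator, so the MRD rate could rise or fall. This stands.

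**Conclusion.** The concern holds in both parts and should be corrected.

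As written, the inferred CRi category omits two of the four platelet/ANC combinations, and the gap reaches the CR/CRi rate, time to CR/CRi, the MRD denominator and RFS. The size is 4 points on the CR/CRi rate per affected patient, assuming 25 evaluable patients and literal coding as non-response. The number affected is unknown and could be zero if every response is documented.

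The interval conflict does not depend on record quality. If the abstract were followed, the interval at 20/25 would be 2.2 times as wide as Clopper-Pearson and would end at 123.6%. At n = 25, any result of 64% or more would give an upper limit above 100%. These Poisson figures assume an intercept-only model, which the abstract does not spell out. If the SAP were followed alone, no interval would be reported for either rate.

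**What to change.** 1. **Protocol Annex 2, List 1 (CRi):** keep the marrow, peripheral blast and extramedullary conditions and change the count condition to platelets <100 ×10⁹/L *or* ANC <1 ×10⁹/L. CRi then takes every patient who meets those conditions without the count recovery required for CR. This changes an endpoint definition only and affects no treatment decision.
2. **Protocol abstract:** delete the reference to exact Poisson regression so that it agrees with section 9.7.
3. **SAP 10.2.3, 10.2.4 and 10.2.11:** state that CR, CRi, CR/CRi and MRD negativity rates are reported with Clopper-Pearson 95% CIs.

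The cost is one word in Annex 2, one phrase in the abstract and one sentence repeated in three places in the SAP. Platelets, ANC and blasts are already collected where response is not recorded, so no new data are needed.
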